4 WEEK EVALUATION: TREATMENT END

Following the final treatment of the entire 4 weeks of study procedure administrations with the Erchonia® GVS, the following will be recorded on the provided case report forms.

- Review of adherence to medication and procedure use, and diet and exercise regime consistency since pre-treatment visit.
- Digital Photographs
- Circumference measurements: waist and hips
- Global Aesthetic Improvement Scale (GAIS): Investigator and Subject
- Body Mass Index (BMI) Calculation
 - Height (in)
 - Weight (kg)
- Subject Satisfaction with Study Outcome
- Subject-Reported perception of Skin Tightness
- Adverse Events assessment

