12 WEEK POST TREATMENT EVALUATION: STUDY EFFICACY ENDPOINT ASSESSMENT

Twelve weeks following the completion of the 4-week treatment administration phase, the following will be recorded on the provided case report forms. These recordings will form the study endpoint data set from which change from baseline will be evaluated with respect to assessing study outcome.

- Review of adherence to medication and procedure use, and diet and exercise regime consistency since prior visit
- Digital Photographs
- Circumference measurements: waist and hips
- Global Aesthetic Improvement Scale (GAIS): Investigator and Subject
- Body Mass Index (BMI) Calculation
 - Height (in)
 - Weight (kg)
- Subject Satisfaction with Study Outcome
- Subject-Reported perception of Skin Tightness
- Adverse Events assessment

STATISTICAL ANALYSIS PLAN

STUDY POPULATIONS

The following two study populations will be evaluated:

1. Intent-to-Treat (ITT) Population

Primary analysis of efficacy will be according to the Intent to Treat (ITT) analysis, including all enrolled subjects.

Missing data for the ITT population will be handled through Last Observation Carried Forward (LOCF) methodology. Sensitivity analysis may be applied if missing data is extensive.

2. Per Protocol Population

Secondary analysis of efficacy to confirm the findings of the primary analysis will be conducted on the per protocol population, comprised of all subjects who completed the study per protocol through to the final treatment administration and outcomes measures recording visit, without incompletes or major protocol deviations or violations.

3. Safety Analysis Population

The Safety Analysis Population will comprise all subjects who were enrolled in the study.

BASELINE VARIABLES AND RECORDINGS

Descriptive summary data for the following baseline variables and recordings will be provided as numbers (n), mean, standard deviation (SD), median, and range (min., max.) for continuous variables and as number (n) and percentage (%) of the total number for categorical variables.

These variables include:

Subject demographics:

- age
- gender
- race
- ethnicity

Subject recordings:

- Baseline body weight (kg)
- Baseline height (m)
- Baseline Body Mass Index (BMI) in kg/m²
- Baseline waist and hip circumference measurements (ins.)

Medication and Procedures

- Current medications (OTC, prescription) taken for/with weight loss indications
- Prior medications (OTC, prescription) taken for/with weight loss indications

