- Procedures undertaken for weight loss indications
- Concomitant medication (OTC, prescription) use for indications other than weight loss

Diet and Exercise

- Daily diet (food and drink consumption)

➤ Exercise patterns

PRIMARY EFFICACY OUTCOME

Primary study efficacy will be evaluated at 12 weeks post-final treatment relative to baseline (pre-treatment).

The primary efficacy outcome for this study is the change in skin laxity at 12 weeks post-final treatment compared to baseline.

Primary efficacy outcome success will be assessed through Blinded Evaluator assignments of before and after subject digital images from each of Baseline and 12 week follow up visits.

Each of three (3) Independent Blinded Evaluators will be presented with coded, deidentified blinded photograph image sets provided in randomized order post-study endpoint. Each Independent Blinded Evaluator will determine and record which image in the pair they believe to represent the before-treatment image (baseline) and which they believe to represent the after-treatment image (12 weeks follow-up). Additional information about the Independent Blinded Evaluators and the image presentation blinding procedure is contained on page 30 of this protocol under the 'STUDY BLINDING' section.

The primary efficacy endpoint for this clinical study will be considered met if at least 2 of the 3 Independent Blinded Evaluators correctly identify the before-treatment (baseline) and after-treatment (12 weeks post-final treatment) photographs for at least 80% of subjects. That is, the study subject responder rate is $\geq 80\%$, with an individual subject responder defined as one whose before- and after-treatment images are correctly identified by ≥ 2 Independent Blinded Evaluators.

Hypotheses

Therefore, the null and alternative hypotheses for the Primary Efficacy Endpoint are the following:

Null Hypotheses: The overall responder rate will be less than 80%.

$$H_0: \mu_A < 80\%$$

Alternative Hypothesis: The overall responder rate will be 80% or greater.

$$H_0: \mu_A \geq 80\%$$

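### LOCF is not a usable missing-data rule for the primary photo-identification endpoint: no earlier score exists to carry forward, and the only images it can supply are the wrong ones

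*Combined protocol and SAP*

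**What the plan says.** Under Study Populations, the Statistical Analysis Plan makes the ITT set primary: "Primary analysis of efficacy will be according to the Intent to Treat (ITT) analysis, including all enrolled subjects". The rule for gaps follows: "Missing data for the ITT population will be handled through Last Observation Carried Forward (LOCF) methodology". After that comes "Sensitivity analysis may be applied if missing data is extensive", with no method named and no definition of extensive. The same section commits to a secondary per-protocol analysis, which leaves out incomplete subjects and major deviations.

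Under Primary Efficacy Outcome, success rests on "Blinded Evaluator assignments of before and after subject digital images from each of Baseline and 12 week follow up visits". Each of three evaluators states which image of a pair is before and which is after. The plan has "an individual subject responder defined as one whose before- and after-treatment images are correctly identified by" at least two of the three evaluators, and the endpoint is met if at least 80% of subjects are responders. That section and Study Blinding both place the scoring after the study endpoint.

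Photographs are scheduled three times: before treatment (Pre-Treatment Outcome Assessments), at the visit headed "4 WEEK EVALUATION: TREATMENT END", and at the 12-week post-treatment visit. The Secondary Efficacy Evaluations instead label the intermediate assessment as four weeks after the final treatment.

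**The concern.** LOCF presupposes an outcome that is measured repeatedly. Here the outcome is a set of evaluator calls made once, on one image pair, after follow-up has ended. A subject without a 12-week photograph has no previous call and no previous responder status. The only thing that could be carried is an image, and the visit schedule offers two:

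- **Lost before the intermediate visit.** The last image is the baseline photograph, so the pair is baseline against baseline. It holds no information on treatment, yet it can be scored as a response.
- **Lost between the intermediate and 12-week visits.** The intermediate photograph stands in for the 12-week image, although Primary Efficacy Outcome defines the pair as baseline and 12-week images.

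If the sponsor meant to carry responder status instead, there is none to carry and the rule is undefined. On any reading, someone has to decide how to classify these subjects after the data exist. The study is single-arm, is intended to support a 510(k) submission, and is decided by one count against one threshold.

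**Working it through.** **Inputs.** Enrolled 35, evaluable 30, possible attrition 15% (Rationale for Sample Size). Success at a responder rate of at least 80%, response being at least 2 of 3 evaluators correct (Primary Efficacy Outcome).

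**The plan's enrolment figure.** 30 × 1.15 = 34.5, rounded up to 35, so 35 is reproduced. The expected number missing is 0.15 × 35 = 5.25, about 5, which leaves 30 completers. The threshold on all enrolled is 0.80 × 35 = 28.

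**A baseline-against-baseline pair.** No option to decline is stated, and presentation order is randomised separately for each evaluator, so each call is taken as an independent guess at 0.5:

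P(at least 2 of 3 correct) = 3 × 0.5³ + 0.5³ = 0.50.

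**Five missing, 24 of 30 completers responding (80%).**

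- All five non-responders: 24/35 = 68.6%, fail.
- All five responders: 29/35 = 82.9%, success.
- Five coin flips: on average 24 + 5 × 0.5 = 26.5, and 26.5/35 = 75.7%, below threshold. Reaching 28 needs at least 4 of 5: (5 + 1)/32 = 18.8%.
- Missing subjects respond at the completers' rate: 24 + 5 × 0.80 = 28, and 28/35 = 80.0%, at threshold.

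With 25 of 30 completers responding, five coin flips reach 28 with probability 16/32 = 50%. With 26 of 30 it is 26/32 = 81.3%.

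**Before any data.** Let p be the true identification rate in completers and q the chance that a missing subject is scored a responder:

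P(success) = Σₓ P(Bin(30, p) = x) × P(Bin(5, q) ≥ 28 − x).

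| p | q = 0 (non-responder) | q = 0.5 (coin flip) | q = p (matches completers) |
|---|---|---|---|
| 0.80 | 4.4% | 35.3% | 59.9% |
| 0.85 | 15.1% | 60.2% | 85.6% |
| 0.90 | 41.1% | 84.5% | 98.0% |

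**Fewer baseline-only subjects.** The documents do not say how dropouts would divide between the two branches. With p = 0.80, m baseline-only subjects and all others complete, P(success) under non-response against coin flip is:

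- m = 1: 46.6% against 54.9%
- m = 2: 32.9% against 49.9%
- m = 3: 20.4% against 44.9%

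**The case against.** Four points can be made for the plan.

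1. **Nothing says a photograph will be paired with itself.** This stands. A reader might infer that the plan instructs evaluators to judge identical images, but the documents do not say so, and Primary Efficacy Outcome confines the pair to baseline and 12-week images. Self-pairing is what a literal LOCF produces. Since that section names the outcome as change in skin laxity, one could also read a carried baseline as zero change and hence non-response. That reading is sensible but unwritten, which leaves the rule undefined.

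2. **There is another safeguard.** This also stands. A reader might infer that the optional sensitivity analysis is the only protection. In fact the per-protocol analysis is a commitment and excludes incomplete subjects. But it is secondary, and by dropping these subjects it neither corrects the primary ITT count nor shows how that count depends on them.

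3. **The range of 68.6% to 82.9% is not an estimate of LOCF bias.** Correct. It is the best-to-worst-case bound for any five missing binary outcomes. The upper end under coin flips has probability 1/32, or 3.1%.

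4. **LOCF does not necessarily favour the device.** Correct. A reader might infer systematic inflation. The table shows coin flips raising P(success) against non-response and lowering it against the assumption that missing subjects match completers.

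The intermediate photograph should also not be described flatly as taken zero weeks after treatment. The visit heading supports that, but the Secondary Efficacy Evaluations label it four weeks after the final treatment. On either label it is not a 12-week image.

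**Conclusion.** The concern holds: LOCF does not give a valid result for the primary endpoint. It has no earlier score to carry, and the images it could supply are either uninformative or at odds with the plan's own definition of the pair.

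At the plan's possible attrition, the treatment of about five subjects can decide the trial. With 24 of 30 completers responding, it moves the result between 24/35 and 29/35 around a threshold of 28/35. The direction is not fixed: at a true completer rate of 0.80, P(success) with five coin-flip pairs is 35.3%, against 4.4% under non-response and 59.9% if missing subjects match completers.

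These sizes assume five missing subjects, independent guessing at 0.5 on identical images, and success judged by the observed 80% rate among all enrolled. The coin-flip figures for five also put every dropout in the baseline-only branch, which is the extreme of an assumed range of one to five. That the rule is unusable rests on none of these assumptions.

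**What to change.** Amend the Statistical Analysis Plan before any photograph is scored:

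- **(a)** For the primary endpoint, a baseline image is never carried forward, and a subject with no post-baseline photograph is a non-responder.
- **(b)** An intermediate photograph is not scored as a 12-week result in the primary analysis. Preferably, a subject without a 12-week photograph counts as a non-responder, and the version using the intermediate photograph is reported as a sensitivity analysis.
- **(c)** Replace the optional sensitivity analysis with a mandatory tipping-point table that counts 0 to m of the m missing subjects as responders and marks where the conclusion changes.
- **(d)** Reconcile the timing label of the intermediate visit between its own heading and the Secondary Efficacy Evaluations.

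Items (a), (c) and (d) need only wording and one small table. Item (b) is a defensible conservative choice with a material price, and is more open to debate. With five missing, 28 of 30 completers (28/30 = 93.3%) must respond, and P(success) is 41.1% even at a true completer rate of 0.90. The sponsor should accept that cost knowingly and put effort into retention. If it prefers another rule, that rule must be written down in advance and must not treat an intermediate image as 12-week evidence.

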- Prior medications (OTC, prescription) taken for/with weight loss indications: dose, frequency of use, duration of use
- Procedures undertaken for weight loss indications: duration since performed
- Concomitant medications (OTC, prescription) routinely taken by the subject for indications other than weight loss: indication, dose, frequency, duration of use

Diet and Exercise

- Details of the subject's typical daily diet (food and drink consumption), including type of diet followed if applicable (e.g. Keto, Vegetarian, Vegan, Pescetarian, high protein, Atkins, Weight Watchers, etc.)
- Typical exercise patterns type (e.g. running, gym, dance classes, walking, etc.) and frequency.

OUTCOME ASSESSMENT TOOLS

OBJECTIVE ASSESSMENTS

- **Body Weight:** recorded in kilograms (kg)
- **Height:** recorded in inches (in)

- **Body Mass Index (BMI):** calculated as the ratio of weight in kilograms to height in meters squared (m²).
- **Waist and Hips Circumference:** Circumference in inches (ins) for the subject's waist and hips will be measured according to the following protocol at all assessments to ensure consistency across the study:
 - ✓ Hip circumference: measurement will be made such that both hip bones are encircled
 - ✓ Waist circumference: distance in inches from the hip bone to the point at which the circumference of the waist is measured (at the subject's natural waist formation) will be recorded after first measurement to allow for consistent post-treatment measurements

Potential inter-investigator variability will be removed through standardization and training of a sole assessor at each test site.

PRIMARY OUTCOME MEASURE

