- Subject agrees to maintain his/her weight (i.e., within 5%) by not making any major changes in diet, exercise or medication routine during the course of the study.
- Subject agrees to refrain from taking any medication(s) or supplements(s), whether prescription or OTC, or undergo any procedures indicated for weight loss, or for fat reduction or improving the appearance of the skin in the abdominal area (e.g. liposuction, ultrasound therapy) for the duration of participation in the clinical study.
- Willing to have research photos taken of treatment areas.
- Understands, and is able and willing to comply with all study visits, treatments and evaluations schedules and requirements.
- Females are at least 9 months post-partum.
- Females are post-menopausal, surgically sterilized, or using a medically accepted form of birth control for at least 3 months prior to the study and agree to continue to do so for the duration of study participation.

EXCLUSION CRITERIA

A subject who satisfies any of the following criteria will be excluded from study participation:

- Skin laxity resulting from genetic disorders, including but not limited to Ehlers-Danlos Syndrome.
- History of undergoing a fat reduction procedure (e.g., liposuction, bariatric surgery, abdominoplasty).
- Botulinum toxin or other aesthetic drug injections within the abdomen area within the past 6 months.

- History of any major prior surgery in the abdominal area
- Implanted medical prostheses (such as clips, pins or plates) in or adjacent to the area of intended treatment.
- Active implanted device such as a pacemaker, defibrillator, or drug delivery system.
- Any clinical and significant dermatological skin condition(s) in the intended abdominal treatment area, such as skin infections or rashes, extensive scarring, psoriasis, etc..
- Tattoo or former tattoo at the treatment area.
- Current moderate to heavy tobacco use, defined as smoking 10 or more cigarettes per day (or equivalent use of other nicotine-containing products such as cigars, pipes, chewing tobacco, or e-cigarettes) within the past 6 months
- History of chronic drug or alcohol abuse.
- Pregnant or intending to become pregnant in the next 6 months.
- Currently enrolled in a clinical study of an unapproved investigational drug or device.

PRE-TREATMENT EVALUATIONS

The following pre-treatment measures will be recorded prior to commencement of the treatment administration phase (prior to treatment administration #1).

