The rationale for selection of the 80% upper limit for study efficacy outcome success determination is based on the outcome of the various clinical studies used to support FDA clearances for various skin laxity and wrinkle reduction claims, including those for the proposed predicate devices for the current intended submission, where applicable, as well as the highest upper limit typically accepted by FDA, with several other successful clearance-supporting trials establishing and reporting upper limits at 70% and others yielding results in the 60% or lower range.

SECONDARY EFFICACY EVALUATIONS

The following five (5) secondary efficacy evaluations will be performed in support of the primary efficacy evaluation. As no claims are intended to be made based on the secondary efficacy outcomes, the findings will be presented descriptively only as numbers (n), mean, standard deviation (SD), median, and range (min., max.) for continuous variables, and as number (n) and percentage (%) of the total number for categorical variables. Statistical analysis of change will not be performed.

1. Aesthetic improvement at 4 and 12 weeks post-final treatment compared to baseline.

Aesthetic improvement at 4 and 12 weeks post-final treatment compared to baseline will be assessed through evaluation of investigator and subject GAIS ratings recorded at each of the respective post-final treatment assessments compared to baseline, with the baseline digital image serving as the baseline reference for determination of post-treatment change. Ratings by subjects and investigator will be assessed separately and in comparison between each other.

2. Change in circumference measurements at 4 and 12 weeks post-final treatment compared to baseline.

Change in circumference measurements recorded for each of the hips and waists separately, and combined, at each of 4 and 12 weeks post-final treatment compared to baseline will be assessed.

3. Change in Body Mass Index (BMI) at 4 and 12 weeks post-final treatment compared to baseline.

Change in Body Mass Index (BMI) in kg/m^2 and its constituent component measurements of height (m) and body weight (kg) at each of 4 and 12 weeks post-final treatment compared to baseline will be assessed.

4. Subject Satisfaction with Treatment Outcome Ratings at 4 and 12 weeks post-final treatment.

Subject satisfaction with treatment outcome ratings recorded at each of 4 and 12 weeks post-final treatment will be assessed and compared.

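### Height is recorded again at both follow-up evaluations, so its measurement error is reported as change and widens the spread of BMI change

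*Combined protocol and SAP*

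**What the plan says.** Under Objective Assessments, height is "recorded in inches (in", weight is recorded in kilograms, and BMI is "calculated as the ratio of weight in kilograms to height in meters squared". Height and weight are listed beneath BMI at the pre-treatment evaluation, at the 4-week evaluation held at treatment end, and at the 12-week evaluation, where the entry reads "Body Mass Index (BMI) Calculation". The record kept for each of the eight treatment sessions does not include height. Of the 12-week recordings the protocol says: "These recordings will form the study endpoint data set from which change from baseline will be evaluated".

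The SAP's secondary evaluation 3 then assesses change in BMI and in "its constituent component measurements of height (m) and body weight (kg", at each of the two follow-up evaluations against baseline. Nothing in the protocol body or SAP says that baseline height is carried into later BMI values. All secondary results are descriptive (n, mean, SD, median, range), with no tests and no claims.

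The weight condition is an inclusion criterion: "Subject agrees to maintain his/her weight (i.e., within 5%) by not making any major changes in diet, exercise or medication routine". It is stated on body weight, not on BMI.

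**The concern.** Subjects are 22 to 70 years old and the study lasts about 16 weeks (4 of treatment plus 12 of follow-up). True height is effectively constant over that time. A difference between two recorded heights is then almost entirely repeat-measurement or rounding error, yet the SAP would tabulate its mean, SD, median and range under an efficacy heading.

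The same error enters BMI through the square of height. A subject whose weight has not moved can show a BMI change, and the SD and range of BMI change mix real weight change with height noise. What is at stake is how clearly one secondary summary can be read, and a row of output that carries no information.

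**Working it through.** The documents give no figure for height error or for the precision of BMI change, so there is no plan figure to reproduce. The body size and error SDs below are assumptions.

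**Shift for one subject.** Assume 80 kg and 1.68 m.
- BMI = 80/1.68² = 28.34 kg/m².
- Height read 1 cm short: 80/1.67² − 28.34 = 0.34 kg/m².
- Height read half an inch short: 80/1.6673² − 28.34 = 0.43 kg/m².
- For comparison, 1 kg of weight is worth 1/1.68² = 0.354 kg/m². A 1 cm height error therefore looks like about 1 kg of weight change.

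**Spread of BMI change.** Assume independent height errors with mean zero and SD s at each of two evaluations, and weight-change SD σ. Then, approximately,

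Var(BMI change) = (σ/H²)² + 2 × (2 × BMI/H)² × s².

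- Weight term, σ = 2 kg: (2/1.68²)² = 0.502.
- Height sensitivity: 2 × 28.34/168 = 0.337 kg/m² per cm.
- Height term: 2 × 0.337² × s², which is 0.057, 0.112 and 0.228 for s = 0.5, 0.7 and 1.0 cm.

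| s (cm) | Variance ratio, formula | Variance ratio, simulation of 400,000 subjects | SD ratio (root of simulated ratio) |
|---|---|---|---|
| 0.5 | 1.11 | 1.11 | 1.05 |
| 0.7 | 1.22 | 1.22 | 1.10 |
| 1.0 | 1.45 | 1.46 | 1.21 |

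The SD of BMI change therefore rises by about 5% to 21%.

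**Dependence on the assumed weight-change SD.** Doubling σ multiplies the weight term by four, to 2.008. The variance ratios become 1 + 0.057/2.008 = 1.03 and 1 + 0.228/2.008 = 1.11, and the SD rises by about 1% to 5%. Halving σ gives a weight term of 0.1255 and variance ratios of 1.45 to 2.82, and the SD rises by about 21% to 68%. Height noise matters most when subjects hold their weight, which is what the protocol asks of them.

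**Effect on the mean.** Errors centred on zero do not shift the mean appreciably. With an assumed height of 66 in, BMI 28 and height-error SD of 0.1, 0.25 or 0.5 in, the SD of spurious BMI change is 28 × 2√2 × s/66 = 0.12, 0.30 or 0.60 kg/m². Dividing by √30 for the planned 30 evaluable subjects gives a standard error of 0.02, 0.05 or 0.11 kg/m².

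**With one baseline height.** H is the same at each evaluation and cancels, so percent change in BMI equals percent change in weight exactly. Body-weight change is identical under either approach.

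**The case against.** The strongest reply is that nothing depends on this. Secondary results are descriptive, no claim rests on them, and the primary endpoint uses photographs alone. Weight change is reported beside BMI change, so a reader who wants the cleaner quantity already has it. All of that stands, and it limits the point to a tidy-up.

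A second reply is that each site has a sole trained assessor. That addresses differences between assessors, not one assessor's error on repeat measurement. The same section gives a repeatable method for waist and hips but none for height.

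A third is that follow-up height might simply be copied from baseline. The text does not say so, and then every height change would be zero by construction. The summary is uninformative either way.

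A reader might go further and infer that height error blurs the trial's check on weight stability. The documents do not support that. The 5% condition is on body weight, weight is recorded directly in kilograms, and its change is reported in its own right, so height error contributes nothing to it. BMI is nowhere named as the stability check. Waist and hip circumference are also listed as objective measures, with their own change evaluation.

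It is similarly tempting to note that a one-inch error moves BMI by 0.88 kg/m², which is 62% of the 1.42 kg/m² that a 5% weight change would produce. That applies a weight limit to BMI and needs a full inch of error; the documents do not state rounding to whole inches.

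**Conclusion.** The point holds as a minor one. Followed as written, the plan reports adult height-measurement error as a secondary efficacy change and adds the same error to BMI change. Under the stated assumptions (80 kg, 1.68 m, height-error SD 0.5 to 1.0 cm per measurement, weight-change SD 2 kg), the SD of BMI change is inflated by about 5% to 21%, or 11% to 46% in variance. The inflation is smaller if weight varies more and larger if it varies less.

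The effect stops at the descriptive height and BMI summaries. There is no material bias in the mean, and no basis for saying that the weight condition, the weight-change results or the primary endpoint is compromised. It is a free improvement, not a defect that threatens a conclusion.

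**What to change.** - Measure height once, at baseline. Convert it from inches to metres by a stated rule (1 in = 0.0254 m) and use that value for BMI at all three evaluations.
- Delete height from the change measures in secondary evaluation 3, and from the treatment-end and 12-week recordings.
- Beside the weight change in kg already planned, report percent change from baseline and the number of subjects beyond the plan's own 5% limit at each follow-up evaluation. The SAP ties no analysis to that limit at present. This is a separate gap that does not depend on height, but it can be closed in the same edit with data already collected.
- While editing the section, reconcile the timing label: the secondary evaluations speak of 4 weeks after the final treatment, whereas the study procedures place the 4-week evaluation at treatment end.

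The cost is a few SAP sentences and matching edits to the two follow-up evaluation lists. It saves one measurement at each of two evaluations and loses no useful information.
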